NIH IRB#: IRB001855

1 PROTOCOL SUMMARY

1.1 Synopsis

- Title:** Hippocampal network changes following mindfulness training in tobacco vaping adolescents in an open-label, pilot study.
- Study Description:** This protocol will use fMRI and in-person and technology-delivered mindfulness-based stress reduction (MBSR) training to elucidate neurobehavioral correlates of regular nicotine vaping in adolescents compared to non-vaping adolescents, and changes in these correlates after MBSR training. Our central hypothesis is that nicotine vaping in adolescents will be associated with impaired hippocampal connectivity with large-scale brain networks (e.g., Executive Control network (ECN), Default Mode Network (DMN), Salience Network (SN)) involved in cognitive control and emotion regulation and decreased state transitions (measured via dynamic resting state functional connectivity (rsFC)); and that MBSR training will increase hippocampal connectivity to ECN and alter time in state and state transitions in frequent vaping adolescents, with these rsFC changes predicting changes in vaping behavior.
- Objectives:** Primary Objectives:
- (1) To characterize static and dynamic rsFC of hippocampal networks in frequent nicotine vaping adolescents compared to non-vaping adolescents.
 - (2) To characterize rsFC changes in hippocampal networks following an in-person and technology-delivered MBSR training program in frequent nicotine vaping adolescents.
- Secondary Objectives:
- To assess engagement with a smoking cessation app and changes in vaping behavior, emotion and cognition in the 3 months following MBSR training.
 - To assess differences between vaping and non-vaping teens pre- and post-MBSR training on other measures of network connectivity.
- Endpoints:** Primary Endpoints:
- (1) Seed-based rsFC between hippocampal seed regions and large-scale brain networks (DMN, ECN, SN) and dynamic-rsFC measures in 40 nicotine vaping and 40 non-vaping youth.
 - (2) Seed-based rsFC between hippocampal seed regions and large-scale brain networks (DMN, ECN, SN) and dynamic-rsFC measures within the nicotine vaping group Pre/Post MBSR training.
- Secondary Endpoint:

Abbreviated Title: Mindfulness and Teen Vaping

Version Date: 07/21/2025

[figure not shown]
NIH IRB#: IRB001855

| | |
|--|--|
| | 
 - Engagement with MBSR training and post-training Craving-to-Quit app and change scores for other behavioral measure (e.g. vaping, emotion regulation). - rsFC from seeds such as dorsal anterior cingulate. |
| Study Population: | 40 nicotine vaping adolescents (13-18 years old) who vape 4-7 days per week, and 40 age, sex, race/ethnicity, SES matched typically developing (TD) adolescents with no nicotine vaping/tobacco smoking history. Participants will be recruited via online advertising, word of mouth, and from our vaping survey study. Recruitment will target the greater Baltimore area. To improve generalizability of our results, we will include youth who vape and who also smoke cigarettes (dual users) or co-use cannabis (co-MJ users) as well as those with stable psychiatric comorbidities. We will measure, control for, and exploratorily examine differences in these behaviors and groups in our analyses. |
| Phase or Stage: | This is a natural history study (comparison of teens who do and do not vape) and an open-label pilot study (comparison of teens who vape before and after MBSR training). |
| Description of Sites/Facilities Enrolling Participants: | The Biomedical Research Center of NIDA-IRP in Baltimore, MD, is the single site used for this study. |
| Description of Study Intervention: | The study intervention is a 9-week MBSR intervention once per week in-person or remotely (via an NIH approved remote platform used in compliance with policy, including HRPP Policy 303). The MBSR will be delivered to groups of 8-12 participants. Only the vaping adolescents will receive MBSR training. |
| Study Duration: | The study duration is approximately 24 months. |
| Participant Duration: | The participant duration is approximately 5.5-7 months, including baseline assessment and MRI scan 1, the 9-week MBSR intervention, and post-intervention assessment and MRI scan 2. There will also be a monthly follow-up for three months after the last MRI scan. Non-vaping participants will only complete baseline assessments and scan 1, which should take a week or less. |

Abbreviated Title: Mindfulness and Teen Vaping
Version Date: 07/21/2025
NIH IRB#: IRB001855

1.2 Schema

Flow Diagram for Nicotine Vaping Adolescent Group and Control Group

Abbreviated Title: Mindfulness and Teen Vaping
Version Date: 07/21/2025
NIH IRB#: IRB001855

1.3 Schedule of Activities

| Procedures | Pre-screening (Pre-consent) | Visit(s) 1 | Visits 2-10 | Visit 11 | Visits 12-15 |
|----------------------------------|--------------------------------|------------|-------------|----------|--------------|
| Eligibility Questionnaire Review | X | X | - | - | - |
| Informed Consent | - | X | - | - | - |
| Demographics | X | X | - | - | - |
| Clinical history | X | X | - | - | - |
| Nursing Eval | - | X | - | X | X |
| Outcome Evaluation | - | - | - | - | - |
| MRI scan | - | X | - | X | - |
| Questionnaires | - | X | - | X | X |
| MBSR training | - | - | X | - | - |
| Adverse Events Reporting | - | X | X | X | X |

Abbreviated Title: Mindfulness and Teen Vaping

Version Date: 07/21/2025

NIH IRB#: IRB001855

| TABLE 1. DIAGNOSTIC MEASURES AND ASSESSMENT BATTERY | | Visit #* | | | |
|--|--|-----------------|--------------|------------|---------------|
| DOMAIN | INSTRUMENT(S) | #1 | #2-10 | #11 | #12-15 |
| Diagnostic Assessment | Mini International Neuropsychiatric Interview for Children and Adolescents-DSM-5.0 version (MINI-KID-5) or SCID-RV | X | | | |
| Demographics and Puberty | Demographics questionnaire and Pubertal Development Scale | X | | | |
| MRI Safety | MRI Safety Assessment | X | | X | |
| Substance Use Measures | General Substance Use: Timeline Follow-back (TLFB) - 28 Days (V1), 7 Days (V12-15): tobacco vaping (vaping days and vapes or puffs/day), tobacco smoking, cannabis, alcohol, other drugs; Substance Use History Questionnaire; Cannabis Use Disorder Test (CUDIT); Craving Questionnaire | X | | | X |
| | E-Cigarette Measures (Vapers only): E-Cigarette Dependence Scale (EDS, 4 items); Modified Fagerstrom Test for Nicotine Dependence (FTND); Nicotine Social Influence Questionnaire (NSIQ) | X | | | X |
| | Biospecimens: Urine Cotinine Test, Urine Drug test (UDT), Breath CO and ALC tests | X | | X | X |
| Psychological Measures | Sensitivity to Reward and Sensitivity to Punishment Questionnaire (SRSPQ), Patient Health Questionnaire-9 (PHQ-9), General Anxiety Disorder-7 (GAD-7), Difficulty in Emotion Regulation Scale, 5-trial Adjusting Delay Discounting Task (bench), Momentary Impulsivity Scale | X | | | X |
| Mindfulness Measures | Five-Facet Mindfulness Questionnaire (FFMQ), Mindfulness Practice Questionnaire (MPQ) (Visits #3-15 only) | X | X (MPQ only) | | X |
| Cognitive Measures | Digit Span (DGS) assessment (forward and backwards) | X | | | X |

***Note:** Visit(s) 1 = Baseline Assessment and MRI scan 1 but may be split into two to four visits (some of which may be conducted virtually) ~0-3 months pre-MBSR intervention; Visits 2-10 = MBSR training; Visit 11 = MRI scan 2 ~0-6 weeks post-MBSR intervention; Visits 12-15 (starting within about 3 weeks post-MBSR training) = monthly follow-up visits (preferably in-person but virtual, if need be); Visit 11 may be combined with Visit 12 or 13 or done separately.

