8.1.2 Screening activities performed after a consent for screening has been signed

At the first visit, after consent/assent is obtained, the following measures will be gathered to further assess eligibility for the study:

Diagnostic Assessment (~1.5 hours)

- a. Clinical history – clinician review
- b. Mini International Neuropsychiatric Interview for Children and Adolescents-DSM-5.0 version (MINI-KID-5) or SCID-RV
- c. MRI Safety Assessment
- a. Substance Use History
 - General Substance Use History Questionnaire (with tobacco & e-cigarette smoking, alcohol, and cannabis questions included)
 - Cannabis Use Disorder Test (CUDIT, 8 items, ~1-2 min)

8.2 Study Evaluations & Procedures after eligibility has been determined.

Administration of questionnaires, interviews, or other instruments (Table 1).

Abbreviated Title: Mindfulness and Teen Vaping

Version Date: 07/21/2025

NIH IRB#: IRB001855

The consent, screening activities listed in 8.1.2, and the baseline assessments listed below may be completed in the same visit virtually or in-person, and all or some of these procedures may also be completed in the same visit as the first scan session. Some questionnaires may be completed virtually in between the consent appointment and Scan Day 1.

Orientation and Initial Baseline Assessments (Visit(s) 1, may be conducted virtually) (~35-55 min):

Demographics and Puberty (~2-5min)

- a. Demographics questionnaire
- b. Pubertal Development Scale

Substance Use Measures

- a. General Substance Use (all participants)
 - Timeline Follow-back (TLFB)
 - Past 28-days tobacco vaping (vaping days and vapes or puffs/day), tobacco smoking, cannabis, alcohol, other drugs if relevant. 7-day TLFB for later visits for vaping teens.
 - Craving Questionnaire (~1-5 min)
- b. E-Cigarette Measures (Vapers only)
 - E-cigarette Dependence Scale (EDS, 4 items, 1 min)
 - Nicotine Social Influence Questionnaire (NSIQ, 1 min)
 - Social influence - peer and family e-cigarette use and approval
 - Modified E-Cigarette Fagerstrom Test for Nicotine Dependence (FTND, 8 items, 1-2 min)

Psychological Measures

- Sensitivity to Reward and Sensitivity to Punishment Questionnaire (SRSPQ, 48 items, 5 min)
- Patient Health Questionnaire-9 (PHQ-9, 9 items, 2 min)
 - Assesses degree of depression severity
- General Anxiety Disorder-7 (GAD-7, 7 items, 2 min)
- Difficulty in Emotion Regulation Scale (36 items, 4 min)
- 5-trial Adjusting Delay Discounting Task (bench, 2 min)

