Within three weeks of the MBSR training completion, vaping participants will complete substance use questionnaires, psychological assessments, mindfulness measures, and cognitive assessments in-person or via secure video call. Our goal is to complete both scan 2 and the initial post-MBSR training assessments within about 1 week after MBSR training. This first follow up visit may be combined with the post MBSR scan 2 but scan 2 may take place as late as approximately 6 weeks after MBSR training to accommodate scheduling. Participants will then have three more follow-up visits, approximately a month apart, in which they complete the measures listed above. These three monthly visits will be dated from the completion of the first assessments following MBSR training (not the scan 2 date). Note: The Digit Span will only be completed at one of the follow up visits, and the FFMQ, DERS and SRSPQ will be completed during two of the visits, preferably the first and the last. The Delayed Discounting questionnaire will only be completed if the follow up visit is in-person. A nursing evaluation consisting of urine sample for a drug test, and breath CO and alcohol test will be taken at each in-person follow-up.

Participants will also engage with the Craving-to-Quit app to elucidate changes in vaping behavior, emotion, and cognition in the 3 months following the MBSR training. The follow-up visits will take about 1 hour each to complete.

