9.4.3 Analysis of the Secondary Endpoint(s)

Our secondary endpoint aims to determine the feasibility and acceptability of the MBSR intervention and thus we will collect descriptive data to determine the feasibility and acceptability via program engagement. To assess program engagement: the # of MBSR group sessions attended will be calculated for each participant and the # and proportion of participants completing 50%, 75%, and 100% of group sessions will be calculated.

To assess preliminary efficacy, we will use the data as described for Primary Endpoint 2. Primary and secondary outcomes for the clinical trial are shown below.

| Outcome Type | Measures Used for Outcome | Definition of Outcome |
|--|---|--|
| Primary Efficacy Outcomes | TLFB, Urine Cotinine Test | The primary outcome measure is change in vaping frequency at the post-MBSR follow-up MRI session. |
| Primary Group Effect Outcome | FFMQ mindfulness scale, Difficulties in emotion regulation scale (DERS), General Substance Use History Questionnaire, Digit Span assessment | The primary outcome measure for the vaping vs TD group comparison will be the substance use, mental health and cognitive function measures at baseline. |
| Secondary Efficacy Outcomes | TLFB, FFMQ mindfulness scale, Difficulties in emotion regulation scale (DERS), Digit Span assessment | Secondary efficacy outcomes are changes in craving, mindfulness, negative emotions (depression, anxiety), emotion regulation and cognitive measures from baseline to post-MBSR study visit. |
| Primary Feasibility/Acceptability Outcomes | Recruitment, retention, program engagement, app use data | MT intervention will be considered acceptable and feasible for use in this population if at least 75% of participants are retained through the EOT, and at least 75% of participants download the C2Q app and complete 1 module. |
| Secondary Feasibility/Acceptability Outcomes | Participant self-report on MBSR program and CTQ utility, ease of use, etc. | Secondary outcomes for feasibility/acceptability are self-report responses about the helpfulness and utility of the MBSR program and C2Q app. |

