9.4.5 Baseline Descriptive Statistics

Tobacco vaping and other drug use measures: Tobacco vaping/e-cigarette use (vaping days, vapes/vaping day) and other drug use in the past 28 days will be collected via TLFB at baseline and post-MBSR MRI follow-up visit. Additional information on time to first vape, nicotine concentration used, vape device used, use of flavors, social influence will be collected along with validated instruments measuring e-cigarette dependence (EDS).

Biochemical measures of drug use: Semi-quantitative urine cotinine testing and carbon monoxide (CO) monitoring will be used to verify self-reported post-MBSR abstinence. Urine drug testing, and breath alcohol level will be collected.

Other self-report assessments: Self-report measures of mood, anxiety, coping, emotion regulation, cognitive function and mindfulness found to show changes following MT in prior studies will be collected and used in theory-driven exploratory analyses.

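### The plan contradicts itself on the recall window and visit used to collect vaping frequency for the efficacy outcome, and states no scale for the change

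*Combined protocol and SAP*

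**What the plan says.** The outcome table in section 9.4.3 names the TLFB and urine cotinine as the measures for the primary efficacy outcome and states: "The primary outcome measure is change in vaping frequency at the post-MBSR follow-up MRI session". The note to Table 1 identifies that session: "Visit 11 = MRI scan 2 ~0-6 weeks post-MBSR intervention".

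Three places describe the TLFB itself:

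- Section 9.4.5: "other drug use in the past 28 days will be collected via TLFB at baseline and post-MBSR MRI follow-up visit".
- Table 1 (section 1.3): "Timeline Follow-back (TLFB) - 28 Days (V1), 7 Days (V12-15". The row is marked at Visit 1 and Visits 12-15, and is blank at Visit 11. Urine cotinine is marked at Visit 11.
- Section 8.2, after describing the 28-day baseline form: "7-day TLFB for later visits for vaping teens".

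Scan 2 need not share a day with a TLFB visit. The note to Table 1 says "Visit 11 may be combined with Visit 12 or 13 or done separately", and section 8.2 says "This first follow up visit may be combined with the post MBSR scan 2".

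Section 9.4.2 says change scores will be computed for vaping frequency, and section 9.4.1 plans paired t-tests. Neither gives a unit, a window or a rule for putting windows of different length on one scale.

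**The concern.** Table 1 is the instrument-level schedule that staff would work from. Followed literally, it does not produce the data that sections 9.4.3 and 9.4.5 rely on. Scaling can be settled at the analysis stage, but uncollected days cannot be supplied then: a 7-day form never yields 28 days, and a TLFB not taken at Visit 11 cannot be reliably recreated.

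The undefined scale adds a second risk. Vaping days is one of the quantities that Table 1 lists for the TLFB. If a count out of 28 were paired with a count out of 7, the difference would be negative whatever the participant did. Its size would be proportional to the participant's vaping rate, so it would also carry into the regression of connectivity change on vaping change planned in section 9.4.2.

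**Working it through.** The plan gives no sample size, power, effect size or SD for vaping frequency (section 9.2 concerns fMRI only), so there is no stated figure to reproduce. The check traces the collection rules and then does the arithmetic.

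**Step 1. The sections side by side**

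| Place | Baseline window | Later window | TLFB at Visit 11? |
|---|---|---|---|
| Table 1 | 28 days | 7 days (Visits 12-15) | No mark |
| Section 8.2 | 28 days | 7 days (later visits) | Not named |
| Section 9.4.5 | 28 days | 28 days | Yes |
| Section 9.4.3 | Not stated | Not stated | Outcome defined there |

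Table 1 and section 9.4.5 conflict on both window and visit.

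**Step 2. Distance from scan 2 to a TLFB, if Visit 11 is separate**

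Visit 12 falls within about 3 weeks of the end of training and scan 2 within 0 to 6 weeks.

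- Visit 12 at week 0 and scan 2 at week 6 are 6 − 0 = 6 weeks apart. Visit 13, about a month after Visit 12 (taken here as 4 weeks), is then 6 − 4 = 2 weeks from the scan.
- Scan 2 at week 0 and Visit 12 at week 3 are 3 − 0 = 3 weeks apart, with no earlier post-training TLFB.

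So even the nearest TLFB can be 2 to 3 weeks from the scan and its cotinine test. Visits 12-15 may also be virtual, and section 8.2 ties the follow-up nursing evaluation to in-person visits.

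**Step 3. Raw vaping days, no true change**

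Let p be the proportion of days vaped. Expected raw change = 7p − 28p = −21p.

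| Unchanged rate | Of 28 days | Of 7 days | Raw change |
|---|---|---|---|
| 10/30 (eligibility floor, section 5.1) | 9.33 | 2.33 | −7 |
| 5/7 | 20 | 5 | −15 |
| 7/7 | 28 | 7 | −21 |

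Each is a spurious fall of 21/28 = 75%.

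**Step 4. Rate scale, no true change**

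Expected change = p − p = 0. Day-sampling SD of the change in days per week = 7 × √[p(1 − p)(1/n₁ + 1/n₂)], assuming independent days. At p = 4/7 (4 days a week, the lower end in the synopsis), p(1 − p) = 0.245:

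| Windows | 1/n₁ + 1/n₂ | SD (days/week) |
|---|---|---|
| 28 and 28 | 0.071 | 0.93 |
| 28 and 7 | 0.179 | 1.46 |
| 7 and 7 | 0.286 | 1.85 |

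**Step 5. Effect on the planned test**

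Simulation of a two-sided 5% paired t-test with 40 vapers, no true change and 5,000 runs. The level, the two-sided test, independent days and p uniform from 1/3 to 1 are assumptions; the documents give none of them. Rejection rates:

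- raw counts, 28 against 7 days: 100%
- the same windows as proportions: 5.5%
- last 7 baseline days against the 7-day follow-up: 5.1%

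**The case against.** The best defence is that the analysis sections agree with each other. Sections 9.4.3 and 9.4.5 together give a 28-day TLFB at baseline and at the defining visit, which is a matched comparison. The general schedule in section 1.3 marks questionnaires at Visit 11, so Table 1 may simply lack a mark, with the 7-day form meant for Visits 12-15. That reading is plausible. However, section 8.2 assigns the 7-day form to later visits without exception, and the general schedule names no instrument, so the documents do not settle it.

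The loss at Visit 11 is also limited. Cotinine, the other named measure, is scheduled there. The visits may be combined, and section 8.2 aims for scan 2 and the first assessments within about a week of training. This stands: the gap arises only when Visit 11 is held separately, which the plan permits.

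Finally, no section plans to subtract a count out of 7 from a count out of 28. Frequency can be read as a rate, and the TLFB also records puffs per day, which does not scale with window length. This stands too, and it makes the −21p artefact conditional.

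**Conclusion.** The documents contradict themselves on the window and visit for the TLFB part of the efficacy outcome, and they leave its scale undefined. This should be settled before further post-training visits, because days not collected cannot be recovered. The size depends on the scale: −7 to −21 days of spurious change on raw counts; zero expected change on a rate scale, with a day-sampling SD of 1.46 rather than 0.93 days per week at 4 days a week (independent days).

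A reader might infer three stronger points that the documents do not support:

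- **That the change score is invalid.** This holds only for raw counts. As a rate, the simulated test is close to its nominal level.
- **That the paired t-test has 2.5 times the variance.** The ratio 0.179/0.071 = 2.5 covers day-sampling error only, under independence. It leaves out between-person variation in true change, for which the plan gives no figure.
- **That the baseline interval ("0-3 months pre-MBSR intervention") is part of the same fault.** Drift over that wait is a separate feature of an uncontrolled open-label pilot. Drift during the nine training weeks is equally uncontrolled, and matching windows would cure neither.

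The label is also inconsistent. Section 9.4.3 calls vaping change a primary efficacy outcome, while the synopsis and section 3 list it as secondary.

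**What to change.** - Mark the 28-day TLFB at Visit 11 in Table 1 and add it to section 8.2, as section 9.4.5 already says.
- In section 9.4.3, define the outcome as change in the proportion of days vaped (or days per week) over the same window at baseline and Visit 11.
- Keep the 7-day form at Visits 12-15 if wanted, for follow-up description, and report it as a rate. If a 7-day value must stand in for the Visit 11 value, analyse it as a rate too.
- State once whether vaping change is primary or secondary, and align the synopsis, section 3 and section 9.4.3.

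The cost is a few more interview minutes at Visit 11 and consistent wording. There is one scientific downside: if scan 2 falls 0 to 1 week after training, a 28-day lookback covers 21 to 28 days of the training period itself. Because the TLFB is recorded by day, the last 7 days at each visit can be reported as a sensitivity analysis. Matching 7 days with 7 days throughout would need no new data, but it is not free: its day-sampling variance factor is 0.286, against 0.179 for the rescaled 28-and-7 comparison and 0.071 for 28 and 28.

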4 STUDY DESIGN

4.1 Overall Design

This is natural history study (comparison of vaping to non-vaping adolescents) and an open label pilot study (MBSR intervention to vaping adolescents).

This single-sight study will be carried out at the NIDA-IRP's Biomedical Research Center in Baltimore, MD.

The study will enroll up to 60 nicotine vaping youth and 60 non-vaping youth to obtain complete data on N=40 tobacco vaping youth 13-18 years old and N=40 age, sex, race/ethnicity, SES matched typically developing (TD) non-vaping/non-smoking youth. The study intervention, given to vaping teens, is a Mindfulness-Based Stress Reduction (MBSR) training. The intervention is a group-based instructor-led mindfulness-based stress reduction (MBSR) training.

Abbreviated Title: Mindfulness and Teen Vaping

Version Date: 07/21/2025

NIH IRB#: IRB001855

The MBSR intervention will consist of eight weekly 2-hour sessions and one 3-hour retreat that will take place at the NIDA BRC. Each group will consist of 8-12 participants.

Participants will be recruited online and via our concurrent vaping survey study. Only nicotine vaping youth will participate in the MBSR intervention. The vaping group will participate in one to four primary data gathering visits, all but one of which can be done virtually. The visit that will include the first MRI scan visit must take place in-person 0-3 months pre-MBSR intervention, and the second MRI scan visit will take place 0-6 weeks post-MBSR intervention. The TD non-vaping group will not participate in the MBSR intervention, and therefore will only participate in the baseline assessments (one to four virtual or in-person visits including the first in-person MRI scan). For those receiving the MBSR intervention, there will also be four monthly follow-up visits which may be administered in-person or virtually. The one at the conclusion of MBSR training may be combined with scan 2. The MBSR visits are optional, and as long as one visit is completed, the other visits if missed will not result in a deviation.

We hypothesize that teens who vape will differ from those who do not on all behavioral, cognitive and imaging measures and that the MBSR intervention will alter these measures in the vaping teens so that they will differ less from their non-vaping counterparts.

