5 STUDY POPULATION

5.1 Inclusion Criteria

In order to be eligible to participate in this study, an individual must meet all of the following criteria:

Non-Vaping group:

1. For adolescents aged 17 and under, parental/guardian informed consent to participate in the study
2. English language fluency
3. Males and females; Age 13-18 enrolled in grades 9-12, or the summer after graduation.
4. No MRI contraindications
5. No evidence of current psychosis, mania, or significant suicidality
6. If on medication for depression, anxiety or ADHD, dose has been stable for 3 months
7. No DSM-5 diagnosis of moderate or severe SUD related to a psychoactive substance, including tobacco, in the past year
8. Access to necessary resources for participating in a technology-based intervention, which includes smartphone ownership for this study
9. No use of nicotine more than 5 times in their life, and none at all in the last 30 days prior to enrollment.

Vaping group:

1. For adolescents aged 17 and under, parental/guardian informed consent to participate in the study
2. English language fluency
3. Males and females; Age 13-18 enrolled in grades 9-12, or the summer after graduation.
4. No MRI contraindications
5. No evidence of current psychosis, mania, or significant suicidality
6. If on medication for depression, anxiety or ADHD, dose has been stable for 3 months
7. No DSM-5 diagnosis of moderate or severe SUD related to another psychoactive substance (other than tobacco) in the past year
8. Vape a nicotine containing product at least 10 days in the past 30 days
9. Access to necessary resources for participating in a technology-based intervention, which includes smartphone ownership for this study

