9 STATISTICAL CONSIDERATIONS

9.1 Statistical Hypothesis

- Primary Endpoint(s):
 - (1) Our central hypothesis is that frequent nicotine vaping in adolescents will be associated with impaired hippocampal connectivity (measured via s-rsFC) with large-scale brain networks (ECN, DMN, SN) involved in cognitive control and emotion regulation and differences in time in state and state transitions (measured via d-rsFC) between. Alternatively, our null hypothesis is that there will be no difference in the hippocampal connectivity or d-rsFC measures between groups (daily nicotine vaping adolescents and TD age-matched adolescents who do not vape).
 - (2) We hypothesize that the MBSR intervention will increase hippocampal connectivity to the ECN and normalize time in state and state transition measures in vaping adolescents, with

these Δ rsFC predicting Δ vaping behaviors. Alternatively, our null hypothesis is that there will be no change in rsFC or vaping behaviors as a result of the MBSR intervention.

- Secondary Endpoint(s):
 - (1) Descriptive statistics will be calculated to determine the feasibility and acceptability of technology-delivered MBSR, while preliminary efficacy to reduce vaping in adolescents will be assessed with t-tests.

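### Baseline vaping may predate MBSR by up to about 3 months with no re-measurement before session 1, so change during the wait, and any regression to the mean, is credited to MBSR

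*Combined protocol and SAP*

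**What the plan says.** **Timing.** The note to Table 1 (1.3) sets baseline and scan 1 at about "0-3 months pre-MBSR intervention; Visits 2-10 = MBSR training; Visit 11 = MRI scan 2 ~0-6 weeks post-MBSR intervention". Section 4.1 repeats that the first scan visit "must take place in-person 0-3 months pre-MBSR intervention". Section 8.2 puts the first post-MBSR behavioural assessment within three weeks of the end of training.

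**Vaping measures.** Table 1 lists "Timeline Follow-back (TLFB) - 28 Days (V1), 7 Days (V12-15"). The only instrument it marks for Visits 2-10 is the mindfulness practice questionnaire. Cotinine and breath CO are taken at Visit 1, Visit 11 and Visits 12-15 (Table 1, 8.2.1). Section 9.4.5 differs on recall: use "in the past 28 days will be collected via TLFB at baseline and post-MBSR MRI follow-up visit". Under either text, nothing is scheduled between Visit 1 and session 1.

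**Entry.** Item 8 of the vaping group criteria in 5.1 is "Vape a nicotine containing product at least 10 days in the past 30 days". The synopsis (1.1) describes vaping on 4 to 7 days per week.

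**Analysis and reading.** Pre-to-post change is tested with paired t-tests (9.4.1, 9.4.2), with no term for waiting time. Non-vapers are measured once (1.1). The null hypothesis for the second primary endpoint is "no change in rsFC or vaping behaviors as a result of the MBSR intervention" (9.1). Section 9.3 likewise assigns participants to an assessment of MBSR's effect on vaping.

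**The concern.** In a single-arm study, the pre-treatment value carries the whole comparison. Here it may be weeks or months old when treatment starts. A teen who cuts down or stops while waiting contributes that change to the vaping change score, and to the end-of-treatment abstinence in 9.4.2, as if it had followed MBSR. An increase during the wait would hide a benefit in the same way.

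Regression to the mean is a second source. Vapers enter on a minimum of recent use, and the Visit 1 recall may cover much of the same month. A baseline that is partly the selection measure tends to be followed by a lower value even if nothing is done.

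The outcome affected is change in vaping frequency, the primary efficacy outcome in 9.4.3, together with the 9.4.2 regressions that relate it to connectivity change. Section 2.2 says the preliminary efficacy data are to inform later controlled trials, so an inflated or masked change would carry into their planning.

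**Working it through.** The plan gives no effect size, SD or sample-size calculation for change in vaping, so there is no figure of its own to reproduce.

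**1. Timeline** (52/12 weeks per month; inputs from 1.3, 4.1, 6.3, 8.2)
- 3-month wait: 3 × 52/12 = 13 weeks.
- Baseline to first post-MBSR behavioural assessment: 13 + 9 + (0 to 3) = 22 to 25 weeks. Share before session 1: 13/25 = 52% to 13/22 = 59%.
- Scan 1 to scan 2: 13 + 9 + (0 to 6) = 22 to 28 weeks. Share: 13/28 = 46% to 13/22 = 59%.
- No wait: 9 to 12 weeks and 9 to 15 weeks.

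**2. Consistency with the stated duration**
- With a 3-month wait: 13 + 9 + (0 to 3) + 13 weeks of follow-up = 35 to 38 weeks, or 8.1 to 8.8 months. Section 1.1 states 5.5 to 7.
- Seven months is 7 × 52/12 = 30.3 weeks. Subtracting 9 of MBSR, 13 of follow-up and 0 to 3 before the first assessment leaves 8.3 to 5.3 weeks of wait.
- On that reading, baseline to first post-MBSR assessment is 30.3 − 13 = 17.3 weeks, of which 5.3/17.3 = 31% to 8.3/17.3 = 48% precedes session 1.

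**3. What any shift not due to MBSR does to the test** (n = 40, two-sided 0.05, paired t, 39 df, noncentrality = shift × √40)

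| Shift, in SDs of the change score | Probability of significance |
|---|---|
| 0.1 | 0.10 |
| 0.2 | 0.24 |
| 0.3 | 0.46 |
| 0.4 | 0.69 |
| 0.5 | 0.87 |

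**4. Regression to the mean alone.** All inputs below are assumptions except the 10-day cut and n = 40. Vaping days per 30 are drawn on two occasions from the same beta distribution, linked by a Gaussian copula with correlation r of 0.6 to 0.9. Those with at least 10 days on the first occasion are kept, and there is no MBSR effect.

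| Assumed source mean and SD (days per 30) | Mean fall (days) | Trials of 40 with a significant reduction |
|---|---|---|
| 12 and 9; 15 and 10 | 0.8 to 3.3 | 16% to 70% |
| 20 to 24 and 7 to 8 | 0.2 to 1.1 | about 4% to 15% |

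The nominal rate in that direction is 2.5%. The second row is there because 4 to 7 days per week is 4 × 30/7 = 17 up to 30 days per 30. A bivariate normal model with other assumed inputs (mean 10 to 18 of 28 days, SD 7 to 8, r 0.5 to 0.85) gave falls of 0.2 to 3.0 days and two-sided rejection in 7% to 70%. These ranges illustrate the problem and are not bounds. Waiting time is not a parameter in either model.

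**5. What a session-1 value would achieve.** It is not the value on which teens were selected. If correlation is equal between all occasions, using it as baseline brings the spurious fall to about 0 and the false-positive rate to 2.5%. If correlation decays with time, one run gave a fall of 1.5 instead of 3.3 days (1.8/3.3 = 55% removed) and false positives of 26% instead of 68%. Both results require that its recall period not overlap the selection window.

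**The case against.** The strongest reply is that this is a declared open-label pilot. The objectives speak of characterising change that follows MBSR, and controlled trials are meant to come later. That stands against asking for a control arm. It does not answer the causal wording in 9.1 and 9.3, or the missing measure at a visit that already takes place.

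It is also fair that a new baseline is a partial remedy. Change from session 1 onward stays uncontrolled, and MBSR visits are optional (4.1), so some session-1 values may be missing. The overlap between eligibility and baseline recall is inferred too: pre-screening precedes consent, Visit 1 may be split, and 8.2 lists the Timeline Follow-back after eligibility. Regression to the mean would be smaller if the two periods differ.

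A reader might infer several stronger points that the documents do not support:
- *Vaping goes unmeasured until Visit 12.* Cotinine and CO are scheduled at Visit 11, and 9.4.5 places a Timeline Follow-back at the post-MBSR scan visit.
- *The simulated false-positive rates measure the harm of the wait.* They come from selection at entry and would arise with no wait at all.
- *Waits will be long because groups must fill.* Group size is stated, but no reason for the window is given, and some waits may be near zero.
- *Teens who quit while waiting become MBSR responders.* No responder is defined; the plan uses change scores and abstinence.
- *Connectivity also regresses to the mean.* Selection is on vaping days, and nothing shows that this carries over to connectivity. Natural change between scans remains possible.

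**Conclusion.** The point holds as a gap in measurement and wording. Vaping may be measured up to about 3 months before MBSR and is not scheduled for re-measurement before session 1, while the whole paired change is attributed to MBSR. Between 31% and 59% of the interval to the first post-MBSR assessment can precede treatment, depending on whether the 7-month duration or the 3-month window governs. For a teen with no wait the share is zero.

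The size and direction of natural change during the wait cannot be derived from the documents. For regression to the mean alone, about 0.2 to 3.3 days per 30 and 4% to 70% significant reductions rest entirely on the assumed means, SDs and correlations. The width of that range is itself a reason to collect the measure. None of this shows that an observed reduction would be spurious. The change proposed is an inexpensive improvement, and the design need not be altered.

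**What to change.** 1. Give a private Timeline Follow-back (individually or by secure form, not in the group) at or just before the first MBSR session attended, with the same recall window as the post-MBSR one. This requires settling the 28-day versus 7-day difference between Table 1 and 9.4.5.
2. Use that value as the pre-MBSR value for the vaping change score. Where it is missing, use Visit 1 and flag it.
3. Report change from Visit 1 to session 1 descriptively, as change before treatment. It should not be called an untreated control, because it absorbs any drop after selection and spans unequal waits.
4. Add a sensitivity analysis of the vaping and connectivity changes by weeks waited. It shows whether change tracks the wait; it cannot separate MBSR from time, since every vaper is treated.
5. In 9.1 and 9.3, replace the causal phrases with: change from before to after MBSR.
6. Reconcile the 0-3 month window with the 5.5 to 7 months in 1.1, and the two descriptions of vaping frequency in 1.1 and 5.1.

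Cost: one short questionnaire at an existing visit, one sensitivity analysis and edits to the text, with no added visits or scans. Downsides: recall windows overlap for teens with short waits, where regression to the mean is only partly removed, and change from session 1 onward remains uncontrolled.
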